7.5.2. SIMPLE KAPPA COEFFICIENT

The agreement between two readers will be calculated using the simple kappa coefficient, i.e. Cohen's kappa. The simple kappa coefficient along with its 95% CI can be obtained by using the FREQ procedure from SAS®.

Document: \\quintiles.net\enterprise\Apps\sasdata\SASa\sas\AVID\18F-AV-1451\Biostatistics\Documentation\SAP\Avid_18F-AV-1451-A16_SAP_Final_v1.0_20180815.docx

Author: XXXXXXXXXX Version Number: Final, v1.0
Version Date: 15Aug2018

Template No: CS_TP_BS016 – Revision 3 Reference: CS_WI_BS005

Effective Date: 01May2012

Copyright © 2012 Quintiles Transnational Corp. All rights reserved.

The contents of this document are confidential and proprietary to Quintiles Transnational Corp. Unauthorized use, disclosure or reproduction is strictly prohibited.

7.5.3. FLEISS' KAPPA

The agreement between the five readers will be calculated using Fleiss' kappa along with its 95% CI (Fleiss 1981).

7.6. EXAMINATION OF SUBGROUPS

The following subgroups will be investigated for the primary efficacy endpoints:

- Age group i.e., <65, ≥65 to <75, and ≥ 75 years
- Birth gender i.e., male and female
- Most recent neurological disease diagnosis i.e., normal, mild cognitive impairment, and dementia
- Atypical tau pathology status i.e., atypical AD tau pathology present in both sides of the brain , atypical AD tau pathology present from either side of the brain, and absent from both side of brain. "Not evaluable" cases will be excluded from this analysis

If the data are too sparse for at least one age subgroup (i.e. less than 5 subjects), the concerned age subgroup will be pooled with another age subgroup, as appropriate. For example, should the <65 years age subgroup has less than 5 subjects, it will be pooled with the ≥65 to <75 years age subgroup yielding to the following two age subgroups: <75 years and ≥75 years.

If the data are too sparse for one of the birth gender, one of the most recent neurological disease diagnosis or one of the atypical tau pathology status subgroup, only descriptive statistics will be provided for that subgroup. That is no statistical inference will be performed.

8. OUTPUT PRESENTATIONS

APPENDIX 1 shows conventions for presentation of data in outputs.

The shells that will be provided with this SAP will describe the presentations for this study and therefore, the format and content of the summary tables, figures, and listings to be provided by IQVIA Biostatistics.

9. DISPOSITION AND WITHDRAWALS

All subjects who provide informed consent, meet all inclusion/exclusion criteria and have received at least one ¹⁸F-AV-1451 injection will be accounted for in this study.

The numbers and percentages of subjects enrolled, who received at least one ¹⁸F-AV-1451 injection, completed the study, and discontinued early from the study as well as the reason for early discontinuation will be summarized based on the ENR overall and by most recent neurological disease diagnosis. For the analysis purpose, study completion will be defined as subjects who died within nine months of their most recent ¹⁸F-AV-1451 PET scan and had an autopsy performed.

Document:	\\quintiles.net\enterprise\Apps\sasdata\SASa\sas\AVID\18F-AV-1451\Biostatistics\Documentation\SAP\Avid_18F-AV-1451-A16_SAP_Final_v1.0_20180815.docx		
Author:	XXXXXXXXXX	Version Number:	Final, v1.0
		Version Date:	15Aug2018
		Reference:	CS_WI_BS005

Template No: CS_TP_BS016 – Revision 3
Effective Date: 01May2012

Copyright © 2012 Quintiles Transnational Corp. All rights reserved.

The contents of this document are confidential and proprietary to Quintiles Transnational Corp. Unauthorized use, disclosure or reproduction is strictly prohibited.

The numbers and percentages of subjects with any critical and/or major protocol deviation (as defined by the clinical team during the course of the study and finalized before database lock) will be summarized based on the ENR overall and by most recent neurological disease diagnosis. The number and percentages of subjects with at least one protocol deviation in each type of protocol deviation will be summarized similarly by severity (critical/major), where type of protocol deviations are:

- Administrative criteria
- Compliance with investigational product
- Concomitant medication criteria
- Eligibility and entry criteria
- Informed consent
- Laboratory assessment criteria
- Other criteria
- Serious adverse event criteria
- Source document criteria
- Study procedures criteria
- Visit schedule criteria

Summaries will be presented in decreasing order of type of protocol deviation within each severity (critical/major). Minor protocol deviations which will be presented in subjects data listing only.

The numbers and percentages of subjects included in/excluded from each analysis set and reasons for exclusion from each analysis set will be summarized based on the ENR overall and by most recent neurological disease diagnosis.

The primary and secondary cause of death as well as clinical events leading up to death with potential to affect autopsy findings (i.e., stroke, brain infection, and other) will be summarized based on the SAF overall and by most recent neurological disease diagnosis.

10. DEMOGRAPHIC AND OTHER BASELINE CHARACTERISTICS

Demographic and other baseline characteristics will be summarized for the SAF overall and by most recent neurological disease diagnosis. A similar summary will be also presented for the EFF1.

The following demographic and other baseline characteristics will be reported for this study:

- Age (years) – calculated relative to the date of the signed informed consent
- Age group (<65, ≥65 to <75, and ≥ 75 years)

Document:	\\quintiles.net\enterprise\Apps\sasdata\SASa\sas\AVID\18F-AV-1451\Biostatistics\Documentation\SAP\Avid_18F-AV-1451-A16_SAP_Final_v1.0_20180815.docx		
Author:	XXXXXXXXXX	Version Number:	Final, v1.0
		Version Date:	15Aug2018
Template No:	CS_TP_BS016 – Revision 3	Reference:	CS_WI_BS005
Effective Date:	01May2012		

- Birth gender
- Race
- Ethnicity
- Highest level of education completed
- Subject handedness
- Weight (kg)
- Height (cm)
- Body mass index (BMI) (kg/m²)
- Childbearing potential
- Alcohol, tobacco, and recreational drug use

Asian sub-race, country of birth and number of years patients lived in the country of birth will be presented in the subjects data listing only.

10.1. DERIVATIONS

- Age (years)= (year of signed informed consent – year of birth) + 1
- BMI (kg/m²)= weight (kg)/ height (m)²

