7.1. Assessment Periods

See Section 11.2, Trial Flow Chart

7.1.1. Screening Visit:

Screening may take place over several days and can occur at multiple locations (e.g. hospice, subject's home, research office, or clinic). All screening assessments will preferably be performed within 45 days prior to the PET imaging session. Some screening assessments may be performed on the imaging day prior to injection with sponsor approval. Screening assessments will include:

- 1. Informed consent (for clinical, imaging and autopsy procedures);
- 2. Obtain historical brain MRI images if available;
- 3. Demographics and baseline characteristics (e.g. birth year, gender, race, ethnicity, education);
- 4. Medical history and concomitant medications;
- 5. Brief physical and neurological exam;
- 6. Neurologic disease history (if relevant: date or months since symptom onset, date or months since diagnosis, family history of neurologic disease);
- 7. Mini-Mental Status Examination (MMSE) may be obtained if the subject is able to cooperate with the test;
- 8. Caregiver or informant to complete IQCODE;
- 9. Urine pregnancy test (for females of childbearing potential);
- 10. Vital signs, including the most recent height and weight which will be collected from subject's previous medical record; and
- 11. A physician or appropriate designee evaluation and summary of current medical status.

7.1.2. ¹⁸F-AV-1451 PET Imaging Visit(s):

- 1. The subject will be seen by a physician prior to dose administration who will assess their ability to safely tolerate the imaging procedure;
- Females of childbearing potential will have a urine (or serum if required by local IRB) pregnancy test prior to injection (the result must be negative for the subject to be administered ¹⁸F-AV-1451);
- 3. A target dose of 370 MBq (10 mCi) of ¹⁸F-AV-1451 will be administered intravenously and a 20-minute continuous brain PET imaging will begin 80 minutes post injection;
- 4. Images will be reconstructed and reviewed immediately after completion of the scan;
- 5. Vital signs will be taken immediately prior to administration of ¹⁸F-AV-1451, and after completion of imaging, prior to discharge;
- 6. Subjects will be observed continuously for signs of adverse events (AE) or serious adverse events (SAE). All AEs and SAEs will be followed until resolution;

- 7. The injection site will be observed for excessive inflammation or damage to the surrounding tissue where the dose was injected; and

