11.1. DERIVATIONS

For subjects who will provide the date of neurological symptom onset and/or the date of neurological disease diagnosis instead of the number of months since neurological symptom onset/neurological disease diagnosis will be computed as follows:

- Number of months since neurological disease symptom onset= [(date of signed informed consent – onset date of neurological disease symptom) + 1]/ (30.4375 days/month)
- Number of months since neurological disease diagnosis= [(date of signed informed consent – date of neurological disease diagnosis) + 1]/ (30.4375 days/month)

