15.1.4. SUBGROUP ANALYSES TO PRIMARY EFFICACY ANALYSES

Primary efficacy analyses #1 and #2 will be repeated for each subgroup specified in Section 7.6.

Document: \\quintiles.net\enterprise\Apps\sasdata\SASa\sas\AVID\18F-AV-1451\Biostatistics\Documentation\SAP\Avid_18F-AV-1451-A16_SAP_Final_v1.0_20180815.docx
 Author: XXXXXXXXXX Version Number: Final, v1.0
 Version Date: 15Aug2018
 Template No: CS_TP_BS016 – Revision 3 Reference: CS_WI_BS005
 Effective Date: 01May2012

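### The SAP age formula adds 1 to the difference in calendar years, so every subject's age is overstated by 1 or 2 completed years and some subjects fall in the wrong age subgroup.

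*SAP*

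**What the plan says.** SAP 10.1 gives the only age formula in either document: "Age (years)= (year of signed informed consent – year of birth) + 1". SAP 10 describes age as "calculated relative to the date of the signed informed consent", so the intended quantity is age at consent.

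Protocol 7.1.1 lists the screening data as "Demographics and baseline characteristics (e.g. birth year, gender, race, ethnicity, education". Birth year is named there, and again in Protocol 7.2; month and day of birth are not.

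The derived age is used in two places:

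- **Demographic tables.** SAP 10 summarises age and age group for the safety set (SAF) and for the first efficacy set (EFF1).
- **Subgroups.** SAP 7.6 sets the bands, "Age group i.e., <65, ≥65 to <75, and ≥ 75 years", and SAP 15.1.4 states that "Primary efficacy analyses #1 and #2 will be repeated for each subgroup specified in Section 7.6".

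SAP 7.6 also has a rule that merges a small band into a different one: "If the data are too sparse for at least one age subgroup (i.e. less than 5 subjects), the concerned age subgroup will be pooled".

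**The concern.** Adding 1 is normal when days are counted inclusively, and the SAP does this in two other places. Study Day in SAP 6.1 adds one day. SAP 11.1 computes months since diagnosis from "date of signed informed consent – date of neurological disease diagnosis) + 1]/ (30.4375 days/month", where the 1 is again one day, added before conversion to months. In SAP 10.1 the unit is the calendar year, so the same 1 adds a whole year. A carried-over day-count convention is a plausible source, but the documents give no reason for it.

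The lack of a full birth date does not justify the addition. A difference in calendar years already errs upward, so adding 1 moves it further from the truth.

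The reported ages of all subjects would be too high, and subjects just below 65 or 75 would be analysed in the band above. Because the shift is always upward, it takes subjects out of the youngest band, which is the one SAP 7.6 uses to illustrate pooling. It could therefore decide whether that band is reported separately.

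**Working it through.** The plan states no numerical age result, so there is no figure to reproduce. The check compares the formula with age in completed years.

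**Inputs.** The formula is from SAP 10.1 and the cut-points of 65 and 75 are from SAP 7.6. Birthdays and consent dates are assumed uniform over the year. The age distributions below are also assumptions, because the documents give none.

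**Step 1: error per subject.** Let D = consent year − birth year.

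| Birthday by consent | Completed age | SAP age | Excess |
|---|---|---|---|
| Passed | D | D + 1 | 1 |
| Not yet passed | D − 1 | D + 1 | 2 |

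Over all 365 × 365 pairs of birth day and consent day, the excess is 1 in 50.1% and 2 in 49.9%. It is never 0, and the mean is 1.5. Without the added 1, the excess is 0 in 50.1% and 1 in 49.9%, mean 0.5. Against exact decimal age, the SAP formula is too high by between just above 0 and just under 2 years, mean 1.0.

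**Step 2: examples.**

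- Born March 1953, consent September 2017: completed age 64 (<65). SAP age 2017 − 1953 + 1 = 65, so the 65 to <75 band.
- Born November 1943, consent September 2017: completed age 73 (65 to <75). SAP age 2017 − 1943 + 1 = 75, so the top band.

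**Step 3: who changes band.** An excess of at least 1 moves everyone with completed age 64 or 74. An excess of 2 also moves those aged 63 or 73, which is about half of them. With P(a) the share of subjects of completed age a:

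- SAP formula: P(64) + P(74) + ½P(63) + ½P(73)
- Plain difference D: ½P(64) + ½P(74)

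**Step 4: size with uniform ages.** Each single year of age then has equal weight.

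| Assumed ages | SAP formula | Plain difference |
|---|---|---|
| 50–95 | 3/45 = 6.7% | 1/45 = 2.2% |
| 60–95 | 3/35 = 8.6% | 1/35 = 2.9% |
| 65–95 | 1.5/30 = 5.0% | 0.5/30 = 1.7% |

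Simulation gives 6.8%, 8.4% and 4.9% with the added 1, and 2.3%, 2.8% and 1.6% without it.

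**Step 5: size with Normal ages.** I simulated 2,000,000 subjects in each of five settings, with means from 72 to 82 and SDs from 10 to 12, truncated at 50 (the minimum age in Protocol 5.3.1).

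- Wrong band: about 6 to 10% with the SAP formula, 2 to 4% with the plain difference.
- Of those truly under 65, about 16 to 28% move up. Of those truly 65 to 74, about 15 to 22% move up.

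**Step 6: subjects.** SAP 3.1 allows up to 74 in the primary efficacy cohort. At 6 to 10% that is 74 × 0.06 = 4.4 to 74 × 0.10 = 7.4 subjects. The added 1 itself accounts for about 4 to 7 percentage points, or 74 × 0.04 = 3.0 to 74 × 0.07 = 5.2 subjects. The rest comes from having only a birth year.

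**The case against.** The strongest reply is that the consequence is narrow. Age enters neither primary endpoint, the efficacy sets have no age criterion, and the success rule uses each reader's confidence limits in the whole set. No success criterion is attached to the age subgroups. All of this is correct, and it limits the importance of the point.

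A second reply is that about 90 to 94% of subjects stay in the right band, and that the shift in effect cuts the bands at about 63.5 and 73.5. The documents give no clinical reason for exactly 65 and 75, and nothing shows that reader accuracy changes near a cut-point. This also stands in part: no change in subgroup sensitivity or specificity has been shown, and an effect on the pooling rule is possible rather than demonstrated. But the tables would still be labelled with cut-points that were not applied, and the age summaries would still be too high.

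Three smaller points are fair:

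- The excess of 1 or 2 years is relative to completed years, which is the usual meaning of age; SAP 10 does not say which meaning it intends.
- That only birth year is available is an inference, because the protocol gives it in a list of examples. The SAP formula uses only years, so the error does not depend on this.
- Some misplacement remains if the 1 is simply dropped. This bears on the choice of remedy, not on whether the formula is wrong.

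**Conclusion.** The concern holds. The formula does not return age in completed years for any subject, and nothing in either document justifies the added year. That part needs no assumption about the age distribution, and neither does the finding that everyone aged 64 or 74 at consent is put in the wrong band.

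The number of subjects affected does depend on the ages actually enrolled. Across the distributions tried, about 5 to 10% are misplaced, and roughly two thirds of that is due to the added 1. The damage is confined to the age summaries for SAF and EFF1, the age-band repeats of the two primary analyses and, possibly, the pooling of a small band. The overall primary analyses and trial success are not affected. It should be corrected, but it does not threaten the trial's conclusions.

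**What to change.** Replace the formula in SAP 10.1 and use the same derivation in SAP 7.6 and SAP 10. There are two options:

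- **Mid-year imputation (preferable).** Set the birth date to the middle of the birth year and take completed years at consent. With t the fraction of the year elapsed at consent, the result is one year too low with probability t when t < ½, and one year too high with probability 1 − t when t ≥ ½. Each case contributes 1/8, so the mean error is zero and the result is wrong for 1/8 + 1/8 = 1/4 of subjects, against about 1/2 with the plain difference. In the Normal-age simulations, 1.0 to 1.8% of subjects are in the wrong band.
- **Plain difference.** Age = consent year − birth year. This is simplest, but it leaves a mean excess of 0.5 year.

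Whichever is chosen, the SAP should say that age is approximate because only birth year is used, and state the direction and size of the remaining error. If full birth dates turn out to be available, completed years can be computed directly.

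The cost is one line of SAP text and one line of code. SAP 4 places the analysis after SAP authorisation, database lock and unblinding, so the change should be made before then, to avoid altering subgroup membership once results are known.

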11. MEDICAL HISTORY

Medical history (including surgical history) and concurrent condition/disease information collected at screening, repeat ¹⁸F-AV-1451 PET scan visit(s) (if any), and autopsy will be classified according to the following categories and coded to system organ class (SOC) and preferred term (PT) using the Medical Dictionary for Regulatory Activities (MedDRA), version 18.1:

- Medical history finding are defined as any findings that stopped prior to the first ¹⁸F-AV-1451 injection;
- Concurrent medical conditions/diseases are defined as any findings that were still present at or started after the first ¹⁸F-AV-1451 injection.

Incidence of medical history findings, surgeries, and concurrent medical conditions/diseases will be presented separately by SOC and PT for the SAF overall and by most recent neurological disease diagnosis. Summaries will be presented by alphabetical order of SOC and decreasing order of total frequency of PT. Subjects with multiple occurrences of the same SOC/ PT will only be counted once per SOC/ PT in the tables.

Family history of Parkinson’s disease, Alzheimer’s disease, dementia with Lewy bodies (DLB), stroke, and

Document:	\\quintiles.net\enterprise\Apps\sasdata\SASa\sas\AVID\18F-AV-1451\Biostatistics\Documentation\SAP\Avid_18F-AV-1451-A16_SAP_Final_v1.0_20180815.docx		
Author:	XXXXXXXXXX	Version Number:	Final, v1.0
		Version Date:	15Aug2018
Template No:	CS_TP_BS016 – Revision 3	Reference:	CS_WI_BS005
Effective Date:	01May2012		

other dementing or movement disorder will be summarized by family relationship for the SAF overall and by most recent neurological disease diagnosis.

Number of months since neurological disease symptom onset and number of months since neurological disease diagnosis will be summarized for the SAF overall and by most recent neurological disease diagnosis. Number and percentage of subjects in each etiology category for the ‘mild cognitive impairment’ and ‘dementia’ most recent neurological disease diagnosis will be summarized for the SAF overall. Number and percentage of subjects who had a previous CSF test (including the Aβ and Tau levels, when available) as well as the number and percentage of subjects who had a previous ApoE test, are ApoE 4 carrier (including the genotype, when available) will be provided for the SAF overall and by most recent neurological disease diagnosis.

All these summaries will be also similarly presented for the EFF1.

11.1. DERIVATIONS

For subjects who will provide the date of neurological symptom onset and/or the date of neurological disease diagnosis instead of the number of months since neurological symptom onset/neurological disease diagnosis will be computed as follows:

- Number of months since neurological disease symptom onset= [(date of signed informed consent – onset date of neurological disease symptom) + 1]/ (30.4375 days/month)
- Number of months since neurological disease diagnosis= [(date of signed informed consent – date of neurological disease diagnosis) + 1]/ (30.4375 days/month)

12. MEDICATIONS

Medications will be classified according to the following categories:

- ‘Prior’ medications are defined as any medications which started and stopped prior to the first ¹⁸F-AV-1451 injection.
- ‘Concomitant’ medications are defined as any medications taken on or after the first ¹⁸F-AV-1451 injection.

APPENDIX 2 describes the handling of partial dates for medications. In the case where it is not possible to determine if a medication is prior or concomitant, the medication will be classified by the worst case; i.e. concomitant.

Medications will be coded to the anatomical therapeutic chemical (ATC) level 3 and preferred drug name using the World Health Organization Drug Dictionary (WHO-DD), version September 2015 C.

Concomitant medications will be summarized by ATC level 3 and preferred drug name for the SAF overall by most recent neurological disease diagnosis. Summaries will be presented by alphabetical order of ATC

Document: \\quintiles.net\enterprise\Apps\sasdata\SASa\sas\AVID\18F-AV-1451\Biostatistics\Documentation\SAP\Avid_18F-AV-1451-A16_SAP_Final_v1.0_20180815.docx

Author: XXXXXXXXXX Version Number: Final, v1.0
Version Date: 15Aug2018
Reference: CS_WI_BS005

Template No: CS_TP_BS016 – Revision 3

Effective Date: 01May2012

Copyright © 2012 Quintiles Transnational Corp. All rights reserved.

The contents of this document are confidential and proprietary to Quintiles Transnational Corp. Unauthorized use, disclosure or reproduction is strictly prohibited.

level 3 and decreasing order of total frequency of preferred drug name . Subjects with multiple occurrences of the same ATC/preferred drug name will only be counted once per ATC/ preferred drug name in the tables. A similar summary will be also presented for the EFF1.

Prior medications will be provided in subjects data listing only.

13. IQCODE AND MMSE

Informant Questionnaire on Cognitive Decline in the Elderly (IQCODE; Jorm 1994) is a short questionnaire designed to assess cognitive decline and dementia in elderly people. The questionnaire is filled out by a relative or friend who has known the elderly person for 10 years or more. To score the IQCODE, the score of each question will be added up and divided by the number of questions i.e., 16. The result is a score that ranges from 0 to 5. A score of 3 means that the subject is rated on average as ‘no change’. A score of 4 means an average of ‘a bit worse’ and a score of 5, an average of ‘much worse’. Should the score of at least one question be missing, the IQCODE score will be set to missing. It will be administered to the subject’s caregiver/informant at screening. The IQCODE score will be summarized using descriptive statistics based on the SAF overall and by most recent neurological disease diagnosis

The Mini-Mental State Examination (MMSE; Folstein *et al.* 1975) is a brief instrument used to assess cognitive function in elderly patients. The instrument is divided into two sections. The first section measures orientation, memory, and attention. The maximum score for the first section is 21. The second section tests the ability of the patient to name objects, follow verbal and written commands, write a sentence, and copy figures. The maximum score for the second section is 9. The MMSE total score is the sum of the score of each section and hence, ranges from 0 to 30. It will be administered at screening to subjects that are able to cooperate with testing. Only the MMSE total score will be captured into the eCRF. Descriptive statistics will be provided for the MMSE total score for the SAF overall and by most recent neurological disease diagnosis.

Similar summaries will be presented for the EFF1.

